5.11.8 Respiratory function

5.11.8.1.1 Parameters

Respiratory parameters are:

- arterial blood gases [ABG]:
 - PaCO2 mmHG
 - PaO2 mmHG
 - HCO3 mEq/L
 - SO2 %
 - Base excess mmol/L
- slow vital capacity [SVC] :
- % of the predicted value for age and sex (%) recalculated

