4.2.2 Measurements of secondary and exploratory variables

4.2.2.1 *Efficacy assessment*

Efficacy assessment will be performed at baseline (V0), 3 months (V3) and 6 months (V4). It will consist of:

- ALSFRS-R score,
- ALS-MITOS score,
- King's College score,
- Assessment of respiratory function: SVC and ABG. Sniff test will be optional, performed in sites that have the equipment and resources to perform it.
- Bioelectrical Impedance analysis

The ALSFRS-R, which compared to ALSFRS includes also respiratory function, is the most widely used and validated rating instrument for monitoring the progression of disability in patients with ALS. It consists of a disease-specific questionnaire with 12 questions aimed at assessing functionality [\[30-32\]](#). Functional decline averages about one point per month in untreated patients [\[33\]](#).

The ALS-MITOS score is a more recent staging system composed by 4 key domains included in the ALSFRS-R (walking/self-care, swallowing, communicating and breathing). It is a validated tool for predicting long-term survival of ALS patients [\[34, 35\]](#).

The King's College score is based on the number of neurological regions affected and requirement for gastrostomy or non-invasive ventilation [\[36, 37\]](#). While ALS-MITOS staging has greater

resolution for late disease stage corresponding to functional impairment, King's College score is able to differentiate early to mid-disease better, making the two systems complementary [38].

The monitoring of respiratory function is achieved by the measurement of SVC, assessed by spirometry: the patient is asked to take a breath as deep as possible, make a tight seal around the device mouthpiece, and then exhale. In SVC assessment, exhalation is performed slowly. SVC is simple, easy to perform and convenient for serial measurements over a long time to evaluate disease progression [39]. Recently, SVC has been chosen more and more frequently over forced vital capacity (FVC) test in ALS clinical trials as it is easier to perform for the patient while providing equivalent information [40]. However, it can be difficult for bulbar-onset ALS patients who experience facial weakness. The sniff test is a simple, portable, inexpensive test that expects patients to inhale through their noses with one nostril occluded and a probe connected to a pressure transducer. This test is easy to perform also for patients with facial weaknesses [39].

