ABG test measures the pH and the levels of oxygen and carbon dioxide in the blood from an artery. ABG is a sensitive and inexpensive tool for monitoring respiratory function in ALS patients, and turned out to correlate with FVC. ABG does not require patient collaboration and is not influenced by bulbar involvement [41]. Arterial blood samples will be drawn through radial arterial puncture into heparin - lithium Vacutainer polyethylene tubes and immediately analysed using blood gas analyser, routinely calibrated, as appropriate.

Bioelectrical Impedance analysis will be performed using the non-invasive device BIODY XPERT^{ZM}, commercialized by Aminogram. The device is maintained by the patient on his ankle, in seated position, during approximately one minute, during which various parameters are recorded and proceeded by a software. All sites will be trained by Aminogram prior to utilization of the device. Once trained, members of the study team will be allowed to train additional members.

4.2.2.2 *Pharmacokinetic assessment*

Blood sampling for PK assessment will be performed at the V2 visit. The day before V2 the patient will go on site to be administered the IMP at 20:00. If the patient cannot come to the hospital on the day before V2, he will take study treatment at home at the time requested by the site (see [Section 4.1.4](#)). The day of V2 the patient will be administered again the IMP at 08:00. The blood samples for PK will be collected in the morning of V2. Patients can, but are not forced to, spend the night at the site between these 2 drug administrations, upon agreement between both parties.

Venous blood samples (10 mL) for the determination of plasma concentrations of IFB-088 and its hydroxylated metabolite IFB-139 will be drawn by direct venipuncture or via an intravenous catheter into heparin - lithium Vacutainer polyethylene tubes (5x2mL). Samples will be collected at the following time points in the morning: pre-IMP dose, 1, 2, 4 and 6 hours post dose. The actual date and time of each blood sample collection will be recorded.

IFB-088 and IFB-139 concentrations will be measured within one week, using a validated high-performance liquid chromatography with tandem mass spectrometry (HPLC/MS-MS) method. After collection, plasma samples will be stored at -80°C pending analyses. Details of PK blood sample processing, storage and shipping procedures will be provided in the LPM provided by the sponsor.

4.2.2.3 *Biomarkers assessment*

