2.2.2 Efficacy Endpoints

- Change in Revised ALS functional rating scale (ALSFRS-R) score from baseline to month 3 and to month 6,
- Worsening according to ALS-Milano-Torino staging system (MITOS) score, i.e. progression to a higher stage at 6 months compared to the baseline,
- Change in King's College score from baseline to month 6,
- Assessment of respiratory function (slow vital capacity [SVC], sniff test [optional], arterial blood gases [ABG]): exploratory endpoint.
- Evaluation of nutritional status and body composition by bioelectrical impedance: exploratory endpoint

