5.11.8.1.3 Analyses

Analyses will be performed on the FAS.

For arterial blood gases:

Descriptive analyses only will be done for parameters assessed at each visit and for change from baseline to V3 and V4.

For the percentage of the predicted value for age and sex of SVC recalculated:

STATISTICAL ANALYSIS PLAN		
InFlectis BioScience	Sponsor: Protocol Number:	InFlectis BioScience P288ALS
VERSION 1.0 NOV 12, 2024		

The change from baseline to Month 6 will be analyzed in an ANCOVA model including terms for treatment and baseline value.

Missing data will be imputed according to strategy of estimand 1:

Missing data will be handled depending on the type of the intercurrent event (i.e.).

- Missing data due to deaths:
 - a) due to disease progression, the % of predicted value at month 6 will be imputed by the worst value (i.e. 0)
 - b) other reason (sudden death included):
 - if the % of predicted value is not missing at Month 3, the % of predicted value at month 6 will be imputed by linear extrapolation given baseline and Month 3 ALSFRS-R score available values.
 - if the % of predicted value is missing at Month3, the % of predicted value at month 6 will be imputed by linear extrapolation based on the predicted value in the linear regression model including terms for intercept and baseline % of predicted value estimated within the treatment group to which the patient is randomized.
- Missing data due to drop-outs or withdrawal will be imputed with the same approach used for handling missing data due to deaths for other reasons (i.e. other than disease progression).

Imputed value lower than 0 will be replaced by 0.

Descriptive analyses will also be done at each visit and for changes from baseline to V3 and V4.

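### Within SAP 5.11.8 only SVC is compared between arms; the listed sniff test gets no summary, and no rule covers a patient who attends V4 but cannot perform SVC

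*SAP*

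**What the plan says.** **Endpoint.** SAP 2.2.2 lists "Assessment of respiratory function (slow vital capacity [SVC], sniff test [optional], arterial blood gases [ABG]): exploratory endpoint". The protocol synopsis (Evaluation criteria) says changes to 3 and 6 months will be calculated for respiratory function, naming SVC, sniff test and ABG. Protocol Table 2 schedules the sniff test at screening, V3, V4 and premature discontinuation, at sites equipped for it.

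**The measures.** Protocol 4.2.2.1 says of SVC: "However, it can be difficult for bulbar-onset ALS patients who experience facial weakness". Of the sniff test it says: "This test is easy to perform also for patients with facial weaknesses". Of blood gases it says: "ABG does not require patient collaboration and is not influenced by bulbar involvement".

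**Analysis.** The parameter list in SAP 5.11.8.1.1 holds five blood-gas items and SVC, the latter as the percentage "of the predicted value for age and sex (%) recalculated". The sniff test is absent. For blood gases, SAP 5.11.8.1.3 states: "Descriptive analyses only will be done for parameters assessed at each visit and for change from baseline to V3 and V4". For SVC: "The change from baseline to Month 6 will be analyzed in an ANCOVA model including terms for treatment and baseline value".

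**Missing SVC.** The same section sets SVC to 0 after death from disease progression and extrapolates after other deaths. It then adds: "Missing data due to drop-outs or withdrawal will be imputed with the same approach used for handling missing data due to deaths for other reasons". No other reason for a missing value is named. SAP 5.11.1.3 leaves missing data to each endpoint, and protocol 8.1.1 has a general rule of no replacement.

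**Declared changes.** SAP section 7 lists the move from MMRM to ANCOVA, with its new handling of deaths, and the removal of the Bayesian analysis. It does not mention the sniff test.

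**The concern.** Every patient in this trial has bulbar-onset disease, so the protocol's caution about SVC applies to the whole population. Entry requires SVC above 60% of predicted, which shows ability at screening; the question is loss of ability over the next six months.

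A patient who attends V4 but cannot perform the manoeuvre is neither dead nor a drop-out. The SAP says nothing about this case, and an ANCOVA omits a record with no outcome. A patient who left the study would therefore be imputed and kept, while one who stayed would be lost. If inability goes with worse decline and is more common in one arm, the SVC comparison is distorted.

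The sniff test could give a second view in exactly these patients. It is collected, but the plan contains no table of it.

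**Working it through.** **1. The plan's own SVC figures.** The equations in SAP 5.2.21 give a predicted volume of 5.789 L for the example man (40 years, 185 cm), so 5 / 5.789 = 86.4% (SAP: 5.79 L, 86%). They give 4.155 L for the example woman (35 years, 170 cm), so 2.5 / 4.155 = 60.2% (SAP: 4.16 L, 60%). Both reproduce, so the derivation of the variable is not in question.

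**2. From listed endpoint to planned analysis.**

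| Measure | Listed in SAP 2.2.2 | Summary in 5.11.8 | Between-arm test in 5.11.8 |
|---|---|---|---|
| SVC % predicted | yes | yes | yes, Month 6 ANCOVA |
| Blood gases | yes | yes | no |
| Sniff test | yes (optional) | no | no |

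**3. Missing-data coverage.** For MITOS and King's stage, SAP Tables 2 and 3 treat a missing Month 6 value as progression whatever the reason. SVC, where inability can be foreseen, has no such catch-all.

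**4. Possible bias.** Let uA and uP be the shares unable to perform SVC on IFB-088 and placebo, and G the extra decline, in percentage points, among those unable. The mean in each arm is then the performers' mean minus u × G, so for unadjusted means:

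bias = (difference in performers) − (difference in all) = (uA − uP) × G

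The documents give neither u nor G, so both are assumed:

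| uA | uP | G = 10 | G = 20 | G = 30 |
|---|---|---|---|---|
| 10% | 10% | 0 | 0 | 0 |
| 10% | 20% | −1 | −2 | −3 |
| 10% | 30% | −2 | −4 | −6 |
| 20% | 10% | +1 | +2 | +3 |
| 30% | 10% | +2 | +4 | +6 |

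A negative sign works against IFB-088 and a positive sign in its favour. With the planned 28 and 14 evaluable patients, 10% of 28 is 2.8 patients and 20–30% of 14 is 2.8 to 4.2, so a few patients are enough.

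**5. Loss of precision.** This arises even with equal inability. With share u missing in both arms, the standard error grows by 1/√(1 − u). As a reference, take the standardised difference with 80% power at 28 and 14 under the SAP's two-sided alpha of 0.20: (1.282 + 0.842) × √(1/14 + 1/28) = 0.695.

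| u (assumed) | Patients left of 42 | SE factor | Power |
|---|---|---|---|
| 0 | 42 | 1.00 | 80.0% |
| 10% | 37.8 | 1.05 | 76.8% |
| 20% | 33.6 | 1.12 | 73.2% |
| 30% | 29.4 | 1.20 | 69.0% |
| 40% | 25.2 | 1.29 | 64.2% |

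**The case against.** Four stronger readings are tempting, and the documents do not support them.

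- **That the SAP excludes these patients.** No sentence says so. The SAP is silent, and omission is an inference from how ANCOVA treats a missing outcome and from the protocol's no-replacement rule.
- **That respiratory function is tested only by SVC.** This is true of section 5.11.8 alone. SAP 5.11.2.4 tests the ALSFRS-R respiratory subscore (items 10–12) by ANCOVA and non-parametrically. It is a rated scale rather than a physiological measure, but it needs no breathing manoeuvre.
- **That the measure suited to this population goes unreported.** The protocol describes two measures as workable despite facial weakness or bulbar involvement. Blood gases, one of them, are summarised. Sniff results will still be listed, since SAP 5.3 lists all data.
- **That the omission pulls the SVC difference towards zero.** The direction depends on which arm has more inability, and step 4 shows both signs.

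It can also be said that the protocol calls SVC difficult, not unobtainable, and blames facial weakness rather than lost respiratory capacity. If inability were unrelated to decline, G would be 0 and only the precision loss would remain. This stands, and it is why the sizes are conditional. Finally, the sniff test is optional and site-dependent within an exploratory endpoint. That limits what the omission costs, but it does not explain leaving collected results without a table or the change undeclared.

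**Conclusion.** The point holds in a limited form. Within SAP 5.11.8 the only between-arm test rests on a measure that the protocol itself treats with caution in these patients. The sniff test is a listed endpoint, with changes promised in the protocol synopsis, yet it has no planned summary and its omission is not declared. The SVC rule leaves one foreseeable kind of missing value uncovered.

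The possible bias is about 1 to 6 percentage points in either direction. That assumes inability of 10% in one arm and 20–30% in the other, 10–30 points of extra decline in those unable, and no baseline adjustment. With equal inability, or inability unrelated to decline, there is no bias. The documents give no rate of inability and no SVC standard deviation, so these are ranges, not predictions. As the endpoint is exploratory, this is a minor improvement.

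**What to change.** 1. **Sniff test.** Add sniff pressure to SAP 5.11.8.1.1 as a descriptive summary by arm at baseline, V3 and V4, with change from baseline, for the sites that performed it. The screening value serves as baseline under SAP 5.2.1.
2. **SVC imputation.** In SAP 5.11.8.1.3, first correct the rule itself: its Month 3 branch extrapolates SVC from ALSFRS-R values, apparently a copying error for SVC % predicted. Then extend the rule to any missing Month 6 SVC in a patient still in the study. Add a sensitivity analysis using the worst observed change, because the regression branch, used when Month 3 SVC is also missing, imputes only the arm's average course.
3. **Reporting.** Give by arm the number of attended V3 and V4 visits without an SVC value, with the reason. Where the reason was not recorded, obtain it through the missing-value queries already described in protocol 13.2, rather than by changing the eCRF this late.

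The cost is SAP wording, small tables from data already collected and some queries, all before unblinding. The downside is a few more imputed values and a sniff summary limited to equipped sites.

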5.11.8.1.2 Expressions

These parameters will be expressed in terms of:

- Value at baseline and at each planned visit (baseline (V0), V3, and V4). Change from baseline to each post baseline visit.

5.11.8.1.3 Analyses

Analyses will be performed on the FAS.

For arterial blood gases:

Descriptive analyses only will be done for parameters assessed at each visit and for change from baseline to V3 and V4.

For the percentage of the predicted value for age and sex of SVC recalculated:

STATISTICAL ANALYSIS PLAN		
InFlectis BioScience	Sponsor: Protocol Number:	InFlectis BioScience P288ALS
VERSION 1.0 NOV 12, 2024		

The change from baseline to Month 6 will be analyzed in an ANCOVA model including terms for treatment and baseline value.

Missing data will be imputed according to strategy of estimand 1:

Missing data will be handled depending on the type of the intercurrent event (i.e.).

- Missing data due to deaths:
 - a) due to disease progression, the % of predicted value at month 6 will be imputed by the worst value (i.e. 0)
 - b) other reason (sudden death included):
 - if the % of predicted value is not missing at Month 3, the % of predicted value at month 6 will be imputed by linear extrapolation given baseline and Month 3 ALSFRS-R score available values.
 - if the % of predicted value is missing at Month3, the % of predicted value at month 6 will be imputed by linear extrapolation based on the predicted value in the linear regression model including terms for intercept and baseline % of predicted value estimated within the treatment group to which the patient is randomized.
- Missing data due to drop-outs or withdrawal will be imputed with the same approach used for handling missing data due to deaths for other reasons (i.e. other than disease progression).

Imputed value lower than 0 will be replaced by 0.

Descriptive analyses will also be done at each visit and for changes from baseline to V3 and V4.

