2.3 Estimands

Table 1. Change in ALSFRS-R from baseline to month 6 (V4)

Objective: To estimate the treatment effect (IFB-088 vs. placebo), on the Change in ALSFRS-R assessed at Month 6.
Estimand: Treatment-Policy Strategy
Treatment: IFB-088 or matching placebo

STATISTICAL ANALYSIS PLAN		
InFlectis BioScience	Sponsor: Protocol Number:	InFlectis BioScience P288ALS
VERSION 1.0 NOV 12, 2024		

ESTIMAND	ANALYSIS
Target population	Analysis set
Patients with bulbar-onset amyotrophic lateral sclerosis	Full Analysis Set (FAS) defined as all randomized subjects who received at least one dose of study treatment (even if discontinued prematurely) with non-missing baseline ALSFRS-R value.
Variable	Outcome measure
Change in ALSFRS-R assessed at Month 6	Mean change
Handling of intercurrent events	Handling of missing data

 • Death related to disease progression • Death not related to disease progression. • Drop-out 
Treatment policy will be applied.
	
 • Estimand #1 (primary estimand): Missing data will be handled depending on the type of the intercurrent event (i.e.). - Missing data due to deaths: 
 a) due to disease progression: the ALSFRS-R score at month 6 will be imputed by the worst value (i.e. 0) b) other reason (sudden death included): 
 - if the ALSFRS-R score is not missing at Month 3, the ALSFRS-R score at month 6 will be imputed by linear extrapolation given baseline and Month 3 ALSFRS-R score available values. Note: in the linear extrapolation at month 6, the timepoint of ALSFRS assessment considered at V3 will be the exact calendar date of V3 assessment. Calendar time of V4 will be considered as 180 days. - if the ALSFRS-R score is missing at Month 3, the ALSFRS-R score at month 6 will be imputed by linear extrapolation based on the predicted value in the linear regression model including terms for intercept and baseline ALSFRS-R score estimated within the treatment group to

STATISTICAL ANALYSIS PLAN		
InFlectis BioScience	Sponsor:	InFlectis BioScience
	Protocol Number:	P288ALS
VERSION 1.0 NOV 12, 2024		

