	
which the patient is randomized. Imputed values will be rounded to the nearest integer. Imputed value higher than 48 will be replaced by 48 and imputed value lower than 0 will be replaced by 0.
 
 - Missing data due to drop-outs or withdrawal will be imputed with the same approach used for handling missing data due to deaths for reasons not related to disease progression. Imputed values will be rounded to the nearest integer. Imputed value higher than 48 will be replaced by 48 and imputed value lower than 0 will be replaced by 0. • Estimand #2: Missing data will be handled depending on the type of the intercurrent event (i.e.). 
 - Missing data due to deaths, whatever the cause: the ALSFRS-R score at month 6 will be imputed by the worst value (i.e. 0). - Missing data due to drop-outs or withdrawal will be imputed with the same approach as for Estimand #1 used for handling missing data due to deaths not related to disease progression. Imputed values will be rounded to the nearest integer. Imputed value higher than 48 will be replaced by 48 and imputed value lower than 0 will be replaced by 0. • Estimand #3: Missing data will be handled depending on the type of the intercurrent event (i.e.). 
 -Missing data due to death whatever the cause: the ALSFRS-R score at month 6
--	--

STATISTICAL ANALYSIS PLAN		
InFlectis BioScience	Sponsor: Protocol Number:	InFlectis BioScience P288ALS
VERSION 1.0 NOV 12, 2024		

	
will be imputed by the worst value (i.e. 0).
 
-Missing data due to drop-outs or withdrawal will be replaced by multiple imputation assuming Missing at random and monotone regression. Note: model for multiple imputation will be done without patient who died before V4.
 
Imputed values will be rounded to the nearest integer.

Population-level summary measure	Analysis approach

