5.2.5 Study visit

If a premature discontinuation visit occurs between [83-99] days after V0 then consider this visit as V3 visit.

If a premature discontinuation visit occurs between [170-194] days after V0 then consider this visit as V4 visit.

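### The SAP imputes missing Month 6 SVC % predicted from ALSFRS-R scores: a carried-over phrase names the wrong variable (minor)

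*SAP*

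**What the plan says.** SAP 5.11.8.1.3 (Analyses, under Respiratory function) plans an ANCOVA of the change in SVC % predicted from baseline to Month 6, with treatment and baseline value as terms. It introduces the missing-data rule with "Missing data will be imputed according to strategy of estimand 1".

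The rule has these parts:

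- Death due to disease progression: % predicted is set to 0.
- Death for another reason, Month 3 % predicted available: "the % of predicted value at month 6 will be imputed by linear extrapolation given baseline and Month 3 ALSFRS-R score available values".
- Death for another reason, Month 3 % predicted missing: a regression prediction with "terms for intercept and baseline % of predicted value estimated within the treatment group".
- Drop-out or withdrawal: handled as death for another reason.

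SAP 2.3, Table 1 (estimand #1) has the same input phrase for the ALSFRS-R total score at Month 6: "imputed by linear extrapolation given baseline and Month 3 ALSFRS-R score available values". It also gives the time convention, namely the actual date of the V3 assessment and "Calendar time of V4 will be considered as 180 days".

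**The concern.** The sentence extrapolates one measure from another. ALSFRS-R is a functional score from 0 to 48, while SVC % predicted is a spirometry percentage on a different scale. A straight line through two ALSFRS-R scores returns an ALSFRS-R number, and nothing in the SAP turns that number into a percentage of predicted SVC.

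The sentence is operative. SAP 5.11.1.3 leaves missing-data handling to each endpoint's own section, and this is the section for SVC. No other section corrects it, and section 7 (changes to the planned analysis) does not mention SVC imputation. A programmer must either follow the text and produce a value with no meaning on the SVC scale, or depart from it without a documented basis. What is at stake is the adjusted SVC comparison at Month 6. The SVC descriptive summaries are not affected, because 5.11.1.3 says missing data are not replaced there.

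**Working it through.** **The text.** The elements of SAP 5.11.8.1.3, side by side:

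| Element | Variable named |
|---|---|
| Heading of the rule | SVC % predicted |
| Value to be imputed | % predicted at Month 6 |
| Condition for the disputed branch | % predicted available at Month 3 |
| Input to the disputed branch | ALSFRS-R score at baseline and Month 3 |
| Input to the companion branch | baseline % predicted |

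Only the fourth row differs, and its wording is that of Table 1. There the input and the imputed variable are both ALSFRS-R, so the phrase is correct.

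**The size, if followed literally.** The plan gives no figure for this point, so there is none to reproduce. All patient values below are assumptions. Days count from V0 = day 0, and ALSFRS-R score is taken as the total score.

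Formula: imputed value = b + (m − b) × f, with f = (180 − t0)/(tV3 − t0). Here b and m are the baseline and Month 3 values, t0 the baseline day, tV3 the V3 day, and 180 the V4 day from Table 1.

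One patient: SVC 85 then 78, ALSFRS-R 40 then 36, tV3 = 91 (week 13), t0 = 0 for simplicity. Then f = 180/91 = 1.978.

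- Own SVC values: 85 − 7 × 1.978 = 71.2
- Literal rule: 40 − 4 × 1.978 = 32.1
- Error: 32.1 − 71.2 = −39.1 points

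**Sensitivity to timing.** SVC is scheduled at screening, which falls 2 days to 2 weeks before V0 (Protocol Table 2 and 4.1.2), so t0 = 0 is slightly off schedule. SAP 5.2.5 counts a premature discontinuation visit on days 83–99 as V3, which is wider than the scheduled days 87–95. For this patient the error is (40 − 85) + (−4 + 7) × f = −45 + 3f:

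| t0 | tV3 | f | Own SVC | Literal | Error |
|---|---|---|---|---|---|
| 0 | 83 | 2.1687 | 69.82 | 31.33 | −38.49 |
| 0 | 99 | 1.8182 | 72.27 | 32.73 | −39.55 |
| −14 | 83 | 2.0000 | 71.00 | 32.00 | −39.00 |
| −14 | 99 | 1.7168 | 72.98 | 33.13 | −39.85 |

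Timing hardly matters: the error stays between −38.49 and −39.85.

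**Sensitivity to the patient** (t0 = 0, tV3 = 91):

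| SVC | ALSFRS-R | Literal | Own SVC | Error |
|---|---|---|---|---|
| 90, 84 | 42, 39 | 36.1 | 78.1 | −42.1 |
| 65, 60 | 47, 46 | 45.0 | 55.1 | −10.1 |
| 62, 50 | 47, 46 | 45.0 | 38.3 | +6.8 |

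Errors are taken before rounding. These are examples, not bounds. Size and sign both depend on the patient.

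**Who is affected.** The branch covers drop-outs and deaths not due to progression with a Month 3 but no Month 6 SVC value. SAP 5.2.5 narrows this: "If a premature discontinuation visit occurs between [170-194] days after V0 then consider this visit as V4 visit". A patient whose SVC was measured at such a visit needs no imputation.

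**The case against.** The strongest reply is that the intent is plain. Every other element of the rule says % predicted, the literal rule has no usable unit, and a competent programmer would use the patient's own SVC values. On that reading the effect is nil and the endpoint is exploratory in any case. This stands, and it is why the point is minor. It does not make the sentence right: the SAP is approved before unblinding as the specification to be programmed, and a wrong input variable should not be left to inference.

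Four stronger readings are tempting, and the documents do not support them.

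- *The sentence contradicts its own lead-in.* The lead-in invokes estimand 1, and Table 1 states estimand 1 with the same ALSFRS-R wording. It points to own SVC values only by inference. The contradiction lies with the heading, imputed variable, condition and companion branch.
- *Only a few patients can be affected, given the 15% drop-out assumption.* That figure is a planning assumption, not a ceiling, and the documents do not say how many drop-outs would have a Month 3 value.
- *The subscore rule in 5.11.2.4 has the same error.* It uses the same phrase, but its target, condition and companion branch all name the subscore, which is part of the ALSFRS-R. The wording is loose rather than wrong.
- *The missing upper limit of 48 proves the intent.* It is weak evidence, because the estimand #3 text in Table 1 also omits the limit although ALSFRS-R is imputed there.

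**Conclusion.** The sentence is wrong as written: it names ALSFRS-R where the rest of the rule requires SVC % predicted, and nothing in the SAP corrects it. Followed literally, it would give the assumed patient about 32% instead of about 71%. That size rests on assumed patient values, and other values change both its magnitude and its direction. Under the evident intent there is no effect.

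A reader might infer that the SVC treatment comparison is biased towards one arm. The documents do not support that: the number affected is not known, the branch applies to both arms, and the sign of the error varies between patients. Nor does the point reach the ALSFRS-R total-score analysis, for which the Table 1 wording is correct, or the primary safety endpoint. SVC is listed as exploratory in SAP 2.2.2. Severity: minor.

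**What to change.** In SAP 5.11.8.1.3, in the branch where Month 3 is available, replace the ALSFRS-R input with: *the available baseline and Month 3 % of predicted values*. Optionally, add a cross-reference to the Table 1 time conventions (actual V3 date, V4 taken as day 180), which at present reach this section only through the mention of estimand 1.

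The cost is one phrase and, if wanted, one cross-reference. No new data and no change of method are needed. If the database is already locked, the correction belongs in the post-lock SAP addendum that SAP section 5 provides for.
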